8.3 Definition of Protocol Deviations

Important protocol deviations and Clinically important deviations are protocol deviations that might significantly affect the completeness, accuracy, and/or reliability of the study data or that might significantly affect a participant's rights, safety, or well-being. These deviations are identified in appendix 17.3 (standalone document), confirmed at the protocol deviation review meeting, and are recorded in the database as such. There will be no separate per-protocol analysis for this study.

9 General Specifications for Data Analyses

9.1 Identification of patients

Patients are identified by their unique subject number taken from the subject ID in their parent study and matched with Classic ID using pre-specified demographic data. If a patient is not matching on at least one demographic variable, this patient will not be included in the analysis.

Table 2: Identification

Unique Subject Identifier	First Previous Study	Previous Clinical Trial
00000256430060001	25643	CLARITY only
00000256430020001	25643	CLARITY/CLARITY EXTENSION
00000288218640003	28821	ORACLE MS

9.2 Dictionary coding

The Adverse events (AEs) and Medical History will be coded with MedDRA v22.1 or higher. Concomitant medications will be upgraded with WHO Drug Dictionary version 2019-September or higher.

9.3 Timepoints

- **Date of First dose of IMP (FDIMP)** is the day of start of first study drug intervention (placebo or cladribine).
- **Date of Last dose of IMP (LDIMP)** is the day of end of study drug intervention (placebo or cladribine). For ORACLE patient both ITP and open label period will be observed to identify the end of study drug intervention.
- **The end of the parent study** is defined as the last date of data collection from the parent study.

- **Baseline** (of parent study) is defined as PSD1 baseline, which is the last assessment prior to or at FDIMP.

9.4 Conversion factors

The following conversion factors will be used:

- 1 year = 12 months = 365.25 days
- 1 month = 30.4375 days

9.5 Handling of missing data/ Presentation of continuous and qualitative variables

It is anticipated that missing/not reported data will feature many of the endpoints, especially BVMT-R and SDMT (see section 14.3.3). No imputation will be done for these assessments.

In general, missing or partial dates will be imputed as follows:

- If year and month available but day is missing, impute day to 15
- If only year available, impute day and month to 15JUN
- If date is completely missing, then no imputation will be done, except for Concomitant Medication end dates: if end date is completely missing (day, month and year) and partial or complete start date then end date will be imputed to be the last study assessment date.

In addition, for concomitant medication dates:

- If imputed start date is after end date, then the start date will be set equal to end date.
- If imputed end date is before start date, then the end date will be set equal to start date.

For time to event analyses, if partial date does not determine whether event occurred before or after start date, then analysis date will be set equal to start date, subject will be censored and time to censoring = 1/365.25.

Continuous variables:

Continuous variables will be summarized using descriptive statistics, i.e.

- number of subjects (N),
- number of subjects with non-missing values,
- number of subjects with missing values
- mean and standard deviation,

- median, 25th Percentile - 75th Percentile (Q1-Q3),
- minimum, and maximum.

Qualitative variables:

Qualitative variables will be summarized by counts and percentages.

There are no plans for any formal statistical inference. This study will adhere to the Guidelines for Good Pharmacoepidemiology Practices (GPP). Data evaluation and interpretation will be based on point estimates and 95% corresponding confidence intervals (CI). Due to the exploratory nature of the study, an adjustment for multiple comparisons is not required.

Analyses will be performed using SAS® Software version 9.4 or higher.

10 Study Participants

The subsections in this section describe the specifications for reporting participant disposition and study discontinuations.

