Time-to-event data will be calculated from first dose of IMP in the parent study and will be presented using Kaplan-Meier estimates or cumulative incidence curves as appropriate. The analytical approach will be further detailed in the SAP.

Genetic variations will be analyzed descriptively. In addition, association of genetic variations with patients experiencing long-term response will be analyzed.

Adverse events will be summarized by number and frequency of patients with events.

Endpoint	Statistical Analysis Methods
Primary	Percentage and 95% CI
Secondary	Percentage and 95% CI
Tertiary/Exploratory	Descriptive statistics and time-to-event analyses as described above

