14.3.2 Durability of clinical outcomes

Durability of clinical outcomes will be summarized descriptively and evaluated via retrospective data collection from medical records or at Study Visit 1:

- Proportion of study participants being bedridden
- Time from first dose of IMP to first use of an ambulatory device
- Time from last dose of IMP to first use of an ambulatory device
- Time from first dose of IMP to first use of a wheelchair
- Time from last dose of IMP to first use of a wheelchair
- Number of MS relapses between the end of parent study to Study Visit 1
- ARR from time of first dose of IMP to SV1, and by 2-year intervals
- ARR from time of last dose of IMP to SV1, and by 2-year intervals
- % and Time to conversion to CDMS (For Cohort D participants only)
- Proportion of study participants diagnosed as Secondary Progressive MS (SPMS) without relapses in the 3 months prior to SPMS diagnosis
- Proportion of study participants diagnosed as SPMS with relapses in the 3 months prior to SPMS diagnosis
- Proportion of study participants diagnosed as Primary Progressive MS (PPMS) (For Cohort D participants only)

Computational rule:

Participants being bedridden, first use of an ambulatory device and first use of a wheelchair are collected on “ambulatory - bedridden status and first use of wheelchair” eCRF page.

Participants diagnosed as SPMS with and without relapses in the 3 months prior to SPMS diagnosis are collected on “History of MS onset” eCRF page and Participants diagnosed as PPMS are collected on “conversion to CDMS” eCRF page.

Time to first ambulatory device/wheelchair

Kaplan Meier curve and estimates including number of subjects at risk, number of subjects with an event and subject censored will be presented for time to first ambulatory and wheelchair from first and last dose of IMP administered, by treatment group (exposed vs never exposed) and overall

Computation rule:

Whichever come first will be considered as an event:

- 1) CRF Ambulatory device page, wheelchair use date
- 2) CRF Ambulatory device page, ambulatory device use date
- 3) EDSS score ≥ 6
- 4) Death due to MS

Kaplan Meier SAS code:

AVAL = time-to-event response variable

CENSOR = censoring variable (0 = event, 1 = no event)

TRT= Trt group (“Exposed to Clad” “Never exposed to Clad”)

Code:

```
PROC LIFETEST DATA=ADTTE OUTSURV=RESULTS ALPHA=0.05 METHOD= KM Conftype =  
Loglog;  
TIME AVAL*CENSOR(1);  
STRATA TRT;  
RUN;
```

Annualized Relapse Rate:

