ARR from time of FDIMP to Study Visit 1 is calculated for each treatment group:

$$\text{ARR} = [(\text{sum of relapses} * 365.25) / (\text{sum of time on study in days until SV1})]$$

ARR from time of FDIMP to Study Visit 1 and by 2-year intervals is calculated for each treatment group:

$ARR = [(sum\ of\ relapses\ *365.25) / (sum\ of\ time\ on\ main\ study\ by\ 2\text{-}year\ intervals\ in\ days\ until\ SV1)]$

Time on study = Study Visit 1 – first dose of IMP +1

ARR from time of last dose of IMP to Study Visit 1 will be calculated similarly.

Table 5: Time window for ARR by 2-year intervals

Cumulative intervals	Time intervals
Less than 2 years	1 to 730 days
2 nd years to 4 th years	731 to 1461 days
4 th years to 6 th years	1462 to 2191 days
6 th years to 8 th years	2192 to 2922 days
X th years to Y th years...	Truncate (X*365.25 +1) to truncate (Y*365.25) days

Time to CDMS (Cohort D only)

Number of participants who converted to CDMS since first and last dose administered will be summarized descriptively.

Both information collected in “Conversion to CDMS” eCRF page and ORACLE MS parent study dataset will be used to identify participants who converted to CDMS after first/last dose of IMP.

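### Subjects whose partial event date straddles the start date are censored at day 1, so any such event that followed the start is lost and early cumulative incidence is biased downward

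*SAP*

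**What the plan says.** SAP 9.5 has general rules for partial dates: "If year and month available but day is missing, impute day to 15" and "If only year available, impute day and month to 15JUN". An event dated this way stays an event. For time-to-event analyses it adds an exception: "if partial date does not determine whether event occurred before or after start date", then the "analysis date will be set equal to start date, subject will be censored and time to censoring = 1/365.25".

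SAP 14.3.2 is the only section with time-to-event code. It specifies Kaplan-Meier curves for "time to first ambulatory and wheelchair from first and last dose of IMP administered", by exposure group and overall. The event is the earliest of wheelchair use, ambulatory device use, EDSS of 6 or more, and death due to MS. Censored records are coded as no event. Protocol 9.4 names one time origin: "Time-to-event data will be calculated from first dose of IMP in the parent study". The last-dose curves are an SAP addition.

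SAP 17.1 marks the Kaplan-Meier table and both figures for the interim analysis as well as the final one. Neither SAP 9.5 nor 14.3.2 gives a reason for the exception, a count of subjects affected, or a sensitivity analysis.

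**The concern.** Censoring is meant for subjects who were event-free when last seen. Here the chart records the event; only its position relative to the start date is unclear. A year-only date is unclear in this sense only when it names the calendar year of the start date. A month-and-year date is unclear only when it names the month of the start date. The rule therefore selects the events closest to the start. Any of them that were incident are the earliest in the curve, so the censoring is informative and the error has one direction.

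The last-dose curve shows the effect. Take a hypothetical subject first dosed in 2009 and last dosed in 2011, whose chart dates first device use only as 2011. From first dose the date becomes 15 June 2011 and counts as an event. From last dose the same record becomes a day-1 non-event.

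First-use dates come from retrospective chart review (Protocol 8.1.1.5 and 8.1.1.6), where Protocol 9.4.1 expects missing data in particular. The tables of events and censored subjects would give no sign that some censored subjects had a recorded event.

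**Working it through.** **1. The plan's own figure.** SAP 9.4 sets "1 year = 12 months = 365.25 days". SAP 14.3.2 measures time on study, for the relapse rate, as Study Visit 1 minus "first dose of IMP +1". With the same convention and the analysis date equal to the start date:

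(start − start + 1)/365.25 = 1/365.25 = 0.00274 years.

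The stated value is exactly day 1.

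**2. What day-1 censoring does in Kaplan-Meier.** Illustration with 100 subjects: 10 have post-start events in the start year with year-only dates, 10 have later events, and 80 are event-free at 12 years.

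| | 1 year | 12 years |
|---|---|---|
| True dates | 10/100 = 10.0% | 20/100 = 20.0% |
| SAP rule | 0.0% | 10/90 = 11.1% |
| Ten subjects deleted | 0.0% | 10/90 = 11.1% |

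The last two rows agree because a record censored at day 1 is in no later risk set. The example shows the mechanism; its event counts are not a forecast.

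**3. Size under stated assumptions.** Inputs from the documents: 587 subjects (the 30% recruitment scenario, Protocol 9.2) and follow-up of around 10 years (Protocol 9). Assumed: constant hazard, start dates uniform over the calendar year, follow-up uniform over 8 to 14 years, no pre-start events, and the share of event dates that are year-only. Means of 400 simulated trials:

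| 10-year risk | Year-only share | Events | Events lost | 1 year: true → rule | 10 years: true → rule |
|---|---|---|---|---|---|
| 10% | 10% | 63.9 | 0.27 | 1.06% → 1.01% | 9.95% → 9.91% |
| 20% | 50% | 127.2 | 3.27 | 2.22% → 1.68% | 19.93% → 19.48% |
| 40% | 100% | 250.4 | 14.78 | 4.96% → 2.51% | 39.91% → 38.36% |

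The 10-year fall runs from 9.95 − 9.91 = 0.04 points to 39.91 − 38.36 = 1.55, about 1.6 points. Mean at-risk time lost is about 0.33 years per affected subject. If only the day is missing (20% risk, half of dates), 0.27 of 128.3 events are lost, with 0.028 years lost per affected subject.

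**4. Ceiling on the 10-year effect.** Under the same constant-hazard assumption with every date year-only, λ = −ln(1 − p)/10, and the probability of a post-start event in the start year is a = 1 − (1 − e^(−λ))/λ. The rule gives (p − a)/(1 − a).

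- p = 12%: λ = 0.01278, a = 0.00636, which is 5.3% of events. (0.12 − 0.00636)/(1 − 0.00636) = 11.4%, a relative fall of 4.7%.
- p = 40%: λ = 0.05108, a = 0.02511. (0.40 − 0.02511)/(1 − 0.02511) = 38.5%, a relative fall of 3.9%.

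**5. Would counting every ambiguous record as an event be better?** The alternative codes each as an event midway between the start and the end of the partial period (20% risk, half of dates year-only; each cell gives 1 year / 10 years):

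| Subjects with a pre-start event | True | SAP rule | Midpoint event |
|---|---|---|---|
| 0% | 2.22% / 19.93% | 1.68% / 19.48% | 2.22% / 19.93% |
| 1% | 2.23% / 19.94% | 1.68% / 19.48% | 2.71% / 20.33% |
| 3% | 2.17% / 19.90% | 1.65% / 19.48% | 3.68% / 21.14% |

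At 3% the midpoint errs by +1.51 and +1.24 points, against −0.52 and −0.42 for the SAP rule. Neither coding is safe as a sole default.

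**The case against.** The best defence is that the rule does the right thing for one of the two possibilities. A subject already using a device before the start was never at risk, and day-1 censoring gives the same curve as excluding that subject. A reader might infer that the rule is wrong whichever way the event fell; the documents do not support that. For pre-start events the only flaw is presentational: a prevalent case appears among those initially at risk and those censored.

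A reader might also infer that about 10 years of follow-up is discarded per subject. It is not. An incident event ends time at risk, so the loss is under one year for a year-only date and under one month when only the day is missing.

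Nor does a large long-term effect follow. Recoding 1 or 2 of 12 events per 100 subjects would give 11/99 = 11.1% or 10/98 = 10.2%, a relative fall of about 7 to 15%. That exceeds the 4 to 5% ceiling in step 4 of the working. A strongly front-loaded hazard could exceed that ceiling, but nothing in the documents supports assuming one.

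Finally, dosing took place inside the parent trials, whose data are integrated (Protocol 4.1, SAP 6.3). SAP 6.2 describes 24 weeks of safety follow-up after the CLARITY-EXT treatment period and after the last dose in ORACLE MS. Dated records may therefore cover much of the time just after dosing, and ambiguous dates may be few.

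All of this stands and limits the size of the problem. It does not rescue the rule for post-start events. The existence of dated trial records is also a reason to use them, which SAP 9.5 does not ask for.

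**Conclusion.** The point holds for the post-start share of ambiguous dates. For those subjects a recorded, early event becomes a non-event, and the device/wheelchair curve can only be biased downward. Under the stated assumptions the loss is 0.04 to 1.6 points at 10 years. It matters more at 1 year, where up to about half of the estimate can go (4.96% to 2.51% if every event date is year-only). These figures rest on a constant hazard, uniform start dates, no pre-start events and an unknown share of year-only dates, so they are a range and not a prediction.

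The importance is minor. One tertiary endpoint is affected, in its interim and final outputs. The primary and secondary proportions do not use this rule, no hypothesis is tested, and the rule is the same in both exposure groups. A reader might infer a bias in the exposed versus never-exposed comparison; the documents give no evidence that ambiguous dates are more frequent in either group.

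**What to change.** Replace the exception in SAP 9.5 with a sequence:

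1. Try to place the event using dated parent-study and retrospective EDSS records. If EDSS of 6.0 or more, or device use, is documented before the start, exclude the subject from the risk set as prevalent. If EDSS below 6.0 is documented at or after the start, count the event within the remaining window, for example at its midpoint.
2. For dates still unresolved, present both codings as bounds: event within the feasible window, and excluded as prevalent.
3. Report the number of subjects handled each way by exposure group, separately for the first-dose and last-dose curves. State the same count for the interim outputs, since SAP 6.4 says the interim results have been disseminated.

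The cost is a short SAP edit and a small programming change, with no new data. The drawback is two curves instead of one wherever unresolved subjects remain. If the count is zero or very small, the report can say so and the bounds will nearly coincide.

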10.1 Disposition of Participants and Discontinuations

Number of subjects screened, number of subjects by parent study treatment group (“never exposed to Cladribine” and “exposed to Cladribine”) will be presented by cohort (A, B, C and D).

Study status (CLASSIC and parent study) will be summarized by cohort, presented as Completed or Discontinued.

Reason for study discontinuation will be summarized.

Time since end of parent study, time since first dose and time since last dose will be summarized in weeks as a continuous variable and in years as categorical for time intervals and in cumulative time intervals with the following categories:

Table 3: Time intervals

Cumulative intervals	Time intervals
Less than 5 years	1 to 1826 days (260 weeks, 5y)
At least 5 years	1827 to 3652 days (521 weeks, 10y)
At least 10 years	3653 to 5478 days (782 weeks, 15y)
At least 15 years	5479 to 7305 days (1043 weeks, 20y)
Etc.	Etc.

10.2 Protocol Deviations/Exclusion from Analysis Populations

Important protocol deviations and Clinically important deviations will be summarized by type of deviation and listed.

11 Demographics and Other Baseline Characteristics

11.1 Demographics

Summaries will be presented by parent study treatment group and total, repeated for each cohort.

The following variables will be based on FDIMP.

- Age at Study Visit 1, continuous years and in categories (≤ 50 y, >50 y)
- Age at parent study baseline, continuous years and in categories (≤ 50 y, >50 y)
- Sex (male, female)
- Race: (White, Black or african american, Asian, Other), other include american indian or Alaska native
- Region: America US, America non-US*, Western Europe, Australia, Eastern Europe, Russia, ROW
*America non-US includes Canada and all countries from South America.
- Disease duration (years)
- Type of MS at screening
- Employment Status
- Education Level
- EDSS at parent studies baseline
- EDSS at Visit 1 (by phone, clinical [site] and their maximum)
- Number of relapses (for CLARITY patients only)
- Prior use of DMD (for CLARITY patients only)
- HDA status (for CLARITY patients only)
- Treatment courses in cohort B
- Long term responders definitions A, B , C, and D
- Type of first DMD after Last IMP dose

The number of subjects by region and country will be summarized on the FAS for each cohort.

Additional analysis:

Using WPS population, the following analyses will be performed to assess potential selection bias:

Comparison of baseline and disease characteristics between CLASSIC participant vs patients who did not participate in the CLASSIC study (and were eligible for CLASSIC study).

Baseline and disease characteristics (at parent study) considered are:

- Age
- Sex
- Region
- Race
- EDSS
- Number of relapses (for CLARITY patients only)
- Prior use of DMD (for CLARITY patients only)
- HDA status (for CLARITY patients only)

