
The study aims to enroll patients from approximately Q3 2019 to Q1 2021. Last Patient Last Visit is expected in Q1 2021 (see Section 4.4 End of Study Definition).

Patient selection bias will be addressed through specific statistical methods (see Section 9 for further details on statistical considerations). Site selection bias will be addressed by robust site feasibility open to all sites that participated in the parent studies.

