8.10 Health Economics

Not Applicable.

9 Statistical Considerations

One interim and 1 final analysis are planned for this study.

Study data will be integrated with study data from the parent studies as required to perform the statistical analyses.

Generally, data will be analyzed descriptively with the following measures: mean with standard deviation, median with interquartile range, minimum and maximum for continuous variables and counts with percentages for categorical variables. Missing data will also be summarized. Patients' demographic factors and clinical characteristics at enrolment will be summarized descriptively as detailed above.

As the study visits are around 10 years after the initial treatment with IMP in the parent studies, it is likely that only a specific type of participants from these trials is available for follow-up. A potential selection bias will be evaluated by comparing the characteristics of those patients randomized to the parent studies and those patients included in this study.

Methodological approaches which evaluate and address this potential selection bias will be further detailed in the Statistical Analysis Plan (SAP). Differences in study populations will be considered when making inferences based upon study results. With this in mind, analyses

will generally be exploratory and for hypothesis generating purposes. Parameter estimates with associated 95% confidence intervals (CIs) will be reported for the study endpoints, as appropriate

The analytical approach for all endpoints is described below and will be further detailed in the integrated Analysis Plan (iAP).

All procedures outlined within this section will be undertaken using a SAS statistical analysis software (version 9.4 or higher).

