Table 15.2.4.4.1	MRI characteristics at Study Visit 2 of long-term responders vs non-responders – Cohort D- MRISS analysis set		
Table 15.2.4.4.2	MRI characteristics at Study Visit 2 of long-term responders vs non-responders – Cohort D – MRISS analysis set (Sensitivity Def B)		
Table 15.2.4.4.3	MRI characteristics at Study Visit 2 of long-term responders vs non-responders – Cohort D – MRISS analysis set (Sensitivity Def C)		

15.2.5: Tertiary Endpoint 1			
Table 15.2.5.1	Real-world treatment patterns in study participants – Cohort A- FAS analysis set		U
15.2.6: Tertiary Endpoint 2			
Table 15.2.6.1	Durability of clinical outcome– Cohort A – FAS analysis set		U
Table 15.2.6.2	Kaplan Meier- Time to first ambulatory device/wheelchair - Cohort A -FAS analysis set	Y	U
Figure 15.2.6.1	Kaplan Meier- Time to first ambulatory device/wheelchair by Exposed/Never Exposed Group - Cohort A -FAS analysis set	Y	U
Figure 15.2.6.2	Kaplan Meier - Time to First Ambulatory Device/Wheelchair - Cohort A - FAS Analysis Set	Y	
15.2.7: Tertiary Endpoint 3			
Table 15.2.7.1	Change in Quality of life outcomes – Cohort A- FAS analysis set	Y	U
Table 15.2.7.2	Change in Cognition outcomes (BVMT-R score)– Cohort D- FAS analysis set		U
Table 15.2.7.3	Change in Cognition outcomes (SDMT score) – Cohort D- FAS analysis set		U
15.2.8: Tertiary Endpoint 4			
Table 15.2.8.1	Change in MRI assessment from Baseline to Study Visit 2– Cohort A -MIRISS analysis set		U
15.2.9: Tertiary Endpoint 5			
Table 15.2.9.1	Responder rate by HDA/Non-HDA patients – Cohort B-FAS analysis set		U
15.2.10: Additional analysis			
Table 15.2.10.1	Additional analysis: Comparison between baseline characteristics from Non-CLASSIC/CLASSIC patients- WPS analysis set		U
15.2.11: PGX Analysis (tables will be repeated for each SNP or combination of SNPs.)			
Table 15.2.11.1.1	Proportion of patients using a wheelchair (EDSS>=7) the majority of the time in the 3 months prior to Study Visit 1 or bedridden – Cohort A – Subgroup with Presence of SNP1 gene - PGX Population		
Table 15.2.11.2.1	Proportion of patients with EDSS of 6.0 or higher since last dose of IMP – Cohort A – Subgroup with Presence of SNP1 gene - PGX Population		

Table 15.2.11.3.1	Clinical characteristics at Study Visit 1 of long-term responders vs Non-Responders – Cohort A– Subgroup with Presence of SNP1 gene - PGX Population		

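### The protocol promises methods that address selection bias, but the SAP only tabulates baseline differences and adjusts no estimate for participation

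*SAP*

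**What the plan says.** Protocol Section 9 (Statistical Considerations) expects selective follow-up about ten years after treatment: "it is likely that only a specific type of participants from these trials is available for follow-up". It then commits the plan to two things, evaluating the bias and addressing it: "Methodological approaches which evaluate and address this potential selection bias will be further detailed in the Statistical Analysis Plan". Protocol Section 4.1 says the same more briefly: "Patient selection bias will be addressed through specific statistical methods".

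The SAP delivers the first of the two. Section 8.1.3 creates the Whole Parent Study (WPS) population, meaning eligible parent-trial patients whether or not they enrolled, for evaluating selection bias. Section 11.1 specifies the analysis as "Comparison of baseline and disease characteristics between CLASSIC participant vs patients who did not participate in the CLASSIC study". The list that follows "Baseline and disease characteristics (at parent study) considered are" has age, sex, region, race and EDSS and, for CLARITY patients only, number of relapses, prior DMD use and HDA status. The output is one table, 15.2.10.1: "Additional analysis: Comparison between baseline characteristics from Non-CLASSIC/CLASSIC patients- WPS analysis set".

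The only adjusted analysis of the primary endpoint (SAP 14.1) is a logistic model with parent study, treatment group and disease duration, fitted to participants. SAP Section 7 states that nothing departs from the protocol's planned analyses.

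**The concern.** Describing a bias and dealing with it are different tasks, and the protocol promised both. The SAP has no participation model, no weighting, no standardisation to the eligible population and no sensitivity analysis for non-participation. Because Section 7 declares no departure, a reader of the study report would not learn that a planned element was dropped.

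The descriptive table is also thinner than it could be. It does not list parent study, parent-study arm or the last EDSS recorded in the parent trial. EDSS carries no time point in the list, but the analysis and the table title both refer to baseline, and SAP 9.3 defines baseline as the last assessment at or before the first dose. SAP 6.3 already names the parent-trial datasets as source data, so all three variables should be obtainable.

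At stake is what the primary proportion means. Without adjustment it describes those who could be enrolled, while the protocol's precision table treats them as a random sample of the parent population.

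**Working it through.** **1. The protocol's precision table.** Protocol 9.2 gives, for a proportion of 10%, half-widths of 2.03, 1.63, 1.33 and 1.08 points at n = 587, 783, 979 and 1,175 (30% to 60% of 1,958). The Wald formula 1.96 × √[p(1−p)/n] gives 2.43, 2.10, 1.88 and 1.72, which do not match. Multiplying by the finite population correction √[(N−n)/(N−1)] with N = 1,958 gives 2.03, 1.63, 1.33 and 1.085. This reproduces the table; the last figure differs only by rounding. The stated precision therefore holds only if participants are a simple random sample of the 1,958, which Protocol Section 9 itself doubts.

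**2. Effect of outcome-related participation.** The documents give no participation rates by outcome, so the odds ratio (OR) of participation, cases versus non-cases, is assumed. Inputs are an observed proportion of 10% (odds 1/9) and a participation fraction s of 0.3 to 0.6, the protocol's scenarios. An odds ratio is symmetric, so the odds of the event among non-participants are (1/9)/OR. With q the corresponding probability:

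eligible-population proportion = s × 10% + (1 − s) × q

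| Assumed OR | q | s = 30% | 40% | 50% | 60% |
|---|---|---|---|---|---|
| 0.5 | 18.2% | 15.7% | 14.9% | 14.1% | 13.3% |
| 0.67 | 14.2% | 13.0% | 12.5% | 12.1% | 11.7% |
| 1.5 | 6.9% | 7.8% | 8.1% | 8.5% | 8.8% |
| 2.0 | 5.3% | 6.7% | 7.2% | 7.6% | 8.1% |
| Stated half-width (points) | | 2.03 | 1.63 | 1.33 | 1.08 |

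Example: OR 0.5 and s = 0.3 give 3.0 + 0.7 × 18.18 = 15.7%.

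The shift from 10% runs from 1.2 points (OR 1.5, s = 60%) to 5.7 points (OR 0.5, s = 30%). It exceeds the half-width at the same recruitment level in all 16 cells, but only narrowly at OR 1.5 (2.17 against 2.03 at 30%). Against the uncorrected Wald half-widths, the OR 1.5 row would not exceed, and OR 0.67 at 60% would be about equal (1.69 against 1.72).

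**3. How much selection is enough.** Take a true proportion of 10%, n = 783, and let r be the participation rate of cases divided by that of non-cases. The observed proportion is 0.1r/(0.1r + 0.9). It differs from 10% by the stated 1.63 points at r of about 0.82 or 1.18.

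**4. The exposed versus never-exposed contrast.** Assume a true risk of 10% in both groups.
- r = 0.7 in both groups: both observe 7.22%, odds ratio 1.00.
- r = 0.8 exposed, 0.6 never exposed: 8.16% and 6.25%, odds ratio 1.33.
- Reversed: odds ratio 0.75.

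The contrast is distorted only when outcome-related participation differs between the groups.

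**The case against.** The plan has several answers, and some of them stand.

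- **Design features reduce selection.** Deceased and lost patients can enter by proxy consent or waiver (Protocol 4.1, 5.1). Telephone EDSS serves patients who cannot attend, including the bedridden (8.1.1.1). Medical records can establish the endpoint, and MS-related death counts as an event (SAP 14.1). These target the loss of disabled patients. Proxy and waiver data depend on local approval, however, and none of these features reaches everyone who is not enrolled.
- **The study is exploratory.** Protocol Section 9 says population differences will be considered in making inferences. That is interpretation, and it does not replace the promised methods.
- **The table may be split by treatment.** SAP 11.1 opens by calling for summaries by parent-study treatment group. Whether this governs the additional analysis is unclear, since that analysis has its own population and a title naming no split. At most it would give exposed versus never exposed, not randomised arm.
- **Other text sounds relevant.** Protocol 9.4 adjusts for which parent study a patient was in, not for whether the patient enrolled. Multiple imputation (Protocol 9.4.1) is optional and concerns gaps in the available data.

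A reader might go further and infer that participation differing by arm would bias every group comparison. It would not: if participation depends on arm alone, risk within each arm is unchanged, and step 4 shows what is needed for bias. A reader might also infer that wheelchair use will be understated, or that the omitted variables are the best predictors of participation. The documents support neither claim: they give no direction of selection and rank no predictors.

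**Conclusion.** The point holds as an undelivered commitment. The protocol promised to evaluate and address selection bias, the SAP only evaluates it, on a limited baseline list, and the gap is undeclared. Under assumed participation odds ratios of 0.5 to 2.0 and the protocol's 30% to 60% scenarios, an observed 10% is compatible with 6.7% to 15.7% in the eligible population, in either direction. That is wider than the sampling error the protocol reports. The figures rest on the assumed odds ratios and show sensitivity; they do not estimate actual bias. Nothing here shows that the primary proportion or the between-group contrast is in fact biased.

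**What to change.** In SAP 11.1, prespecify a participation model in the WPS population. Fit it separately by parent study, or with parent-study-specific terms, because relapses, prior DMD and HDA are listed for CLARITY patients only. Use arm, age, sex, region, race, and baseline and last on-trial EDSS, plus those three variables for CLARITY.

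In SAP 14.1 and 14.2.1, report inverse-probability-of-participation weighted (or standardised) proportions with robust 95% CIs for the primary and EDSS ≥ 6 endpoints, as a sensitivity analysis beside the unweighted ones.

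Add parent study, arm and last on-trial EDSS to Table 15.2.10.1 and show it by arm. If no adjustment is adopted, SAP Section 7 should at least declare the departure.

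The cost is some programming on parent data already named as a source, and some precision. Assume, for example, 80% of patients with low last EDSS (5% risk, 45% participation) and 20% with high (30% risk, 20% participation). The unweighted proportion is (0.8 × 0.45 × 5% + 0.2 × 0.20 × 30%)/0.40 = 7.5%, and the weighted one is 10.0%. The effective sample size is 1,958/(0.8/0.45 + 0.2/0.20) = 705 of 783. Weighting does not remove unmeasured selection, and for patients at parent sites that do not join it relies on extrapolation.
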